2.3 Endpoints

- 2.3.1 Endpoint for primary objective: (1) Placebo response (defined as > 20% reduction in pain intensity following placebo treatment, or defined from pain app ratings using permutation with 0.05 p-value cut-off) versus active treatment response (reduction in pain intensity following naproxen/omeprazole treatment)
- 2.3.2 Endpoints for secondary objective: (1) Testing the specificity and sensitivity of the brain and behavioral parameters from Phase 1, in combination with the TOPPP developed from the study interviews, as predictive markers for response in Phase 2. These parameters will be considered validated if together are at least 80% accurate in stratifying responders from non-responders.
- 2.3.3 Endpoint for gender objective: (1) Testing for females showing higher incidence of placebo response using combined outcomes from phase 1 and phase 2 data.

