2.0 STUDY OBJECTIVES

2.1 Primary and Secondary Objectives

- 2.1.1 To evaluate the interaction between placebo response and active treatment in individuals classified as placebo responders vs non-responders. Individuals in the No Treatment group will be used as a negative control to control for regression to the mean, duration of pain, and other potential confounds.

Hypothesis: Brain functional and anatomical properties between groups after 6 weeks of treatment will identify separate circuitry for placebo analgesia and active treatment analgesia; and these groups will show distinct time courses and magnitudes of analgesia.

- 2.1.2 To test and validate brain imaging and personality parameters identified in Phase 1 that predict the propensity for placebo response and use the results to classify participants into responders vs non-responders before study intervention.

Hypothesis: Brain- and behavioral- based parameters identified as markers of placebo response in the first phase of the study will accurately predict potential responders from non-responders at first scan. The classification before study intervention will closely correspond to the responses observed at the end of treatment period.

- 2.1.3 To identify gender dependence of placebo analgesia propensity and examine brain and personality gender differences that underlie the seeming higher propensity of females for placebo response.

Hypothesis: Sexual dimorphism of the human brain and behavioral/personality differences may have a potential interaction effect and predisposition on placebo propensity. We expect to identify gender-specific biomarkers that are sexually dimorphic with regard to placebo response.

- 2.1.4 Classification of placebo responders versus non-responders for 2.1.2 will be based on Equation 1 below:

$$p = (e^{f(x)}) / (e^{f(x)} + 1)$$

$$f(x) = -3.3586 + 1.6676 * \text{Maia_Emotion} - 0.2127 * \text{Erq_Suppress} + 34.8608 * \text{sign_permutation}$$

where a probability (p) <0.5 = predicts non-responder and a probability (p) ≥0.50 predicts responder.

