2.2 Exploratory Objectives

Self-report data from Phase 1, in the form of questionnaire answers and interview answers, will be used to develop and validate a self-measurement Tool for Placebo Propensity (TOPPP) to be tested here in Phase 2. Additionally, biomarkers for placebo response identified in Phase 1 will be validated in this phase via the initial stratification into predicted responders versus non-responders at the beginning of the study.

Specifically, the brain circuits we observe for placebo propensity reflect interactions between the lateral prefrontal cortex and pain processing areas, (this is now confirmed from Phase 1 results), and these pain and disease properties should be readily identified in personality, expectation, and medical exposure appraisals (measurements we collected from specific questionnaires; emotional responses seem to best capture placebo propensity in Phase 1 results), as well as captured from themes and patterns seen in qualitative interview responses (this data remains to be analyzed from Phase 1 data) from the previous phase. Significant differences in questionnaire scores (total scores and/or specific subscores) between placebo responders and non-responders, as well as qualitative and quantitative differences seen between these groups in their responses to interview questions, will inform us as to which variables we should use in our new tool (we now have such a tool from Phase 1 results) that may have predictive capacity. This tool will be used in combination with brain biomarkers in the second phase to help stratify participants into responders versus non-responders at the first scan, using all new CBP participants as a validation group.

This multi-method approach maximizes the likelihood that we will identify self-report variables uniquely linked to the placebo response and its neural signature by including items that capture the unique characteristics of chronic back pain and their treatment effects, spanning the disease continuum and producing scores calibrated onto a common metric. Importantly, a system that meets these needs is likely to be accepted and routinely used in clinical and research settings.

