Phase 1 results identify a robust simple model based on personality that predicts placebo. We will use this or some small variant as our primary personality model to be validated in Phase 2. Additionally, we have kept some other questionnaires that should trend in being predictive and we can test their contribution in the larger cohort in Phase 2.

8.2.7: Predictive Model/Classifier from Brain/Questionnaire Parameters:

The final model from Phase 1 will be used to categorize participants into responders and non-responders. The mathematical details can be found on Page 10, and the identification will be a 1:1 ratio as mentioned in section 5.2.1. This then provides a robust validation for the generalizability of the model.

8.2.8: Language/Interview Analysis:

We will record patient interviews over 4 visits (visits 1, 2, 4, and 5). The first will be a short interview consisting of questions found on pages 44-45. In the remaining visits we will ask patients to describe 1 of a set of 3 pictures (randomly selected for each visit).

All audio and text files will be de-identified with the participant's subject id. Transcripts will be pre-processed according to standard Natural Language Processing (NLP) procedures, including parsing, lemmatizing, and stemming the data. Pre-processed, tokenized text will undergo basic language analyses including calculations of verbosity, unique vocabulary, lexical diversity, and other syntactic and morphological parameters (Hess et al., 1984) that can be used as features of interest or as general quality control measures.

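### The documents conflict on which model the 80% validation rule judges: the endpoint adds an interview-based tool that Equation 1 does not contain

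*Combined protocol and SAP*

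**What the plan says.** **Endpoint (2.3.2).** Sensitivity and specificity are tested for the Phase 1 brain and behavioral parameters "in combination with the TOPPP developed from the study interviews". The success rule is: "These parameters will be considered validated if together are at least 80% accurate in stratifying responders from non-responders". No denominator, confidence interval or formula for the combined score is given.

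**Classifier (2.1.4).** "Classification of placebo responders versus non-responders for 2.1.2 will be based on Equation 1 below". Objective 2.1.2 is the one that 2.3.2 serves. The equation has an intercept, three printed coefficients and a 0.5 cut ("where a probability (p) <0.5 = predicts non-responder"). Its inputs are MAIA emotion, ERQ suppression and the connectivity value.

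**How it is applied (5.2.1).** Between Visits 2 and 3 a blinded assessor with no participant contact enters those three inputs, obtains the class and sends it to the pharmacy, which holds a separate randomization sequence for each class.

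**Analysis plan (8.2.6 and 8.2.7).** For the combined brain and questionnaire classifier, 8.2.7 says "The final model from Phase 1 will be used to categorize participants into responders and non-responders". For the questionnaire-only model, 8.2.6 says "We will use this or some small variant as our primary personality model to be validated in Phase 2", and adds that other retained questionnaires can be tested in Phase 2.

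**The TOPPP (2.2, 8.2.6).** Section 2.2 says the tool comes from Phase 1 self-report and interview data. It says of the interview material that "this data remains to be analyzed from Phase 1 data", and shortly afterwards that the tool is already in hand. Section 8.2.6 links the TOPPP to MAIA and ERQ items.

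**The concern.** A pass/fail rule for validation is meaningful only if one model, fixed before outcomes are seen, is scored on the new patients. Read literally, 2.3.2 scores Equation 1's ingredients plus an interview tool with no written form, while the classification that drives randomization uses Equation 1 alone. If the combined score were assembled, or a variant chosen, once Phase 2 responses were known, its accuracy in those same patients would be biased upward. Passing 80% would then not show that Phase 1 markers predict response in new patients, which is the claim in objective 2.1.2.

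**Working it through.** **1. Which model does each section point to?**

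| Section | Model | Interview term? | Fixed in advance? |
|---|---|---|---|
| 2.3.2 | Phase 1 parameters plus TOPPP, judged jointly | Yes, as worded | No formula given |
| 2.1.4, 5.2.1 | Equation 1 | No | Yes: coefficients and cut printed, applied before treatment |
| 8.2.7 | Final Phase 1 model | None mentioned | Yes |
| 8.2.6 | Personality model or a near version of it | No | Not fully |

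The personality model and Equation 1 already differ. The Phase 1 summary in 1.3 lists MAIA not-worry among three personality predictors, and Equation 1 omits it.

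**2. Denominator.** The 80% figure has no stated inputs, so there is nothing to reproduce. I assume accuracy is scored in placebo completers. From 5.3: 210 × 3/7 = 90 randomized to placebo, and 90 × 140/210 = 60 completers. The rule then needs 0.80 × 60 = 48 correct.

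**3. One locked model.** P(pass) = P(X ≥ 48), with X ~ Binomial(60, p):

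| True accuracy p | 65% | 70% | 75% | 80% | 85% |
|---|---|---|---|---|---|
| P(pass) | 0.9% | 5.7% | 23% | 58% | 89% |

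At 90% to 94% it exceeds 99%. With all 90 placebo patients (72 of 90 needed) it is 2.2% at p = 70% and 17% at p = 75%.

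**4. Best of K variants chosen after outcomes are known.** Each variant has the same true accuracy. Whether a given patient is classified correctly is correlated across variants through a latent normal variable. The rule is passed if the best variant has at least 48 correct. Results are by simulation; the independent case is 1 − (1 − q)^K, with q taken from step 3.

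| p | Latent correlation | K = 1 | K = 3 | K = 5 |
|---|---|---|---|---|
| 75% | 0.95 | 23% | 36% | 41% |
| 75% | 0.9 | 23% | 38% | 45% |
| 75% | 0.6 | 23% | 46% | 58% |
| 75% | independent (upper bound) | 23% | 55% | 73% |
| 70% | 0.95 | 5–6% | 10% | 13% |
| 70% | independent (upper bound) | 5.7% | 16% | 25% |
| 65% | 0.6 | 0.9% | 2% | 3.5% |

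**5. Refitting instead of choosing.** I simulated 60 patients (50% responders, the share expected in 8.1.1), one true score and k pure-noise predictors, with the logistic model refitted and scored on the same patients. Each cell has 1,500 runs.

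| p | Locked | k = 2 | k = 5 | k = 10 |
|---|---|---|---|---|
| 70% | 5–6% | 9% | 19% | 41% |
| 75% | 23% | 35% | 46% | 69% |

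With 0 to 2 added terms the gain is about 0 to 12 points (largest: 35 − 23 = 12). It becomes large only when several features are added.

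**The case against.** The strongest reply is that a locked validation is already there. Equation 1 is printed with its coefficients, is tied by 2.1.4 to the objective in question, is computed blind before treatment and determines which randomization sequence is used, so it can be audited. Section 2.1.2 frames the hypothesis as agreement between that classification and later response, and 8.2.7 leaves no latitude. If the TOPPP is simply the MAIA and ERQ part, as 8.2.6 suggests, then combining it with brain markers is Equation 1 itself, and the interview phrase may be outdated. All of this stands, and it is why the point is a conflict in the text rather than a flaw in the design.

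It does not remove the conflict. On the questionnaire reading, the statement that the tool was developed from interviews is wrong. On the interview reading, the score is undefined. Either way 2.3.2 needs an edit.

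A reader might also infer that the endpoint itself permits variants, or that the sponsor plans to tune the model on Phase 2 data. The documents support neither. The variant wording is in 8.2.6 and concerns the personality model, not 2.3.2. Section 2.2 derives the TOPPP from Phase 1 data. The language models to be built under 8.2.8 are not linked to the 80% rule.

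**Conclusion.** The concern holds as an unresolved conflict over which model the 80% rule judges, with later fitting or selection left open rather than planned. It cannot be said that the validated model will differ from the one used to classify; the text allows both readings.

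The size depends on assumptions the plan does not supply: 60 placebo completers, true accuracy, number of variants and how closely they agree. Near versions of a three-term model would probably agree closely, so the 0.95 rows are the more cautious guide. There, the best of three or five raises the chance of passing from 23% to 36% or 41% at true accuracy 75%, and from 5–6% to about 10% or 13% at 70%. At 65% the inflation is small in absolute terms. Because the rule is a stated success threshold, this is more than missing detail.

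**What to change.** In 2.3.2 and 8.2.7, state that the 80% rule applies only to the Equation 1 classification sent to the pharmacy before Visit 3, with the printed coefficients and 0.5 cut unchanged. Name the patients who count in the denominator. In 8.2.6, label personality-model variants exploratory, and do the same for any interview-based TOPPP and the language models in 8.2.8. Report their accuracy with cross-validation. In 2.2, reconcile the two statements on whether the tool exists.

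The cost is wording only: no change to data, procedures or sample size, and the variants can still be reported. If the true accuracy is near the 94% reported from Phase 1, the locked model passes more than 99% of the time, so little is given up.

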11. PUBLICATIONS -----27

12. REFERENCES -----28

13. SUPPLEMENTS/APPENDICES ----- 32

 I CONSENT FORM TEMPLATE ----- 32

 II LIST OF QUESTIONNAIRES ----- 40

 III AE COLLECTION FORM TEMPLATE ----- 41

 IV DSMP ----- 42

 V STUDY ROSTER -----111

 VI SCHEDULE OF EVALS & ASSESSMENTS ----- 114

 VII BIostatistician CV ----- 117

 VIII LABORATORY PROCEDURES & EVALUATIONS ----- 126

STUDY SCHEMA AND DESIGN

Design Schema for Objective 2 (Phase 2):

We intend to randomize 210 CBP patients into the study with the expectation that 140 will finish successfully. The entire duration of the study will be 12 weeks with an initial 3-week baseline period (visits 1-3), a 6-week treatment period (visits 3-5), and a final 3-week washout period (visits 5-6). During the baseline period eligible **participants will be predicted as placebo responders and non-responders** based upon baseline brain scan results and specific questionnaire answers (properties determined from the results of **Phase 1**) and then classified on that basis. Participants will then be randomized within each classification group (placebo responders and placebo non-responders) at a ratio of 3:3:1 such that 42.5% receive active medication (naproxen/omeprazole, 500/20mg, bid), 42.5% receive matching placebo treatment and 15% no treatment. Brain imaging, self-report questionnaire, and pain/mood rating measurement regimens are shown in **Figure 1**. Pain, mood, and pill ingestion will all be monitored by smart phone for the duration of the study, as well as determined in person at each visit.

[figure not shown]

Figure 1. Experimental schema for Phase 2. Expected changes in pain are shown in solid and dashed horizontal lines. We expect to see different pain outcomes for the various placebo and treatment combination groups. To be noted, we predict that the No Treatment group will have similar pain trajectory as those classified Non-responders and treated with placebo. As well, in the No Treatment group participants will be classified as placebo responders and placebo non-responders, but will not receive any treatment agent, therefore, their pain trajectory will be constant throughout the study.

STUDY SUMMARY

Title	BRAIN MECHANISMS FOR CLINICAL PLACEBO IN CHRONIC PAIN
Short Title	PLACEBO IN CHRONIC PAIN (PICP)
Protocol Number	Grant:
Phase	Grant Phase 2
Methodology	Double blind, randomized (see section 5.4 for more specifics on blinding)
Study Duration	12 weeks
Study Center(s)	Northwestern University

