responses are across these studies, and how they are sustained for the entire study duration. In all three studies placebo decreases pain by at least 10% within 2-4 weeks and then by an additional 10-30% within 3 months. In **figure 3** (Cox2 NSAID study), placebo treatment decreased CBP pain by >50% in approximately 35% of the group. To unequivocally state that these are placebo responses, it is necessary to have a no-treatment, observation only, control group. Nonetheless, **figure 3** strongly suggests that the placebo effect may be dichotomous, hinting at the notion of two groups: responders and non-responders—this very notion is consistent with our preliminary results. Thus, *if we can identify chronic pain patients who will respond to placebo, then we can potentially decrease the pain in this group by about 30-50%, which would be highly clinically significant.*

Figures 2 and 3 also illustrate an important property of clinical placebo, namely a sustained relief from pain for many weeks. In contrast, experimental placebo studies, by design, only examine very short duration (hours to a few days) effects. Thus, brain circuitry identified for experimental placebo is unlikely to generalize to the clinically observed placebo effects. To our knowledge, using brain circuitry to predict the placebo response in the clinical setting has not been studied outside of our lab.

The current study design specifically addresses aspects of placebo trial design that have received ethical and scientific criticism. A recent review identifies 9 distinct potential sources of bias in placebo effect studies (Hrobjartsson et al., 2011). To circumvent these problems, we rely on randomized controlled trials (RCTs) and within-subject control washout periods, perform all procedures identically across all groups, all preliminary analyses are done blinded, un-blinding occurs only after the completion of data collection, and all primary outcomes are objective brain parameters. By controlling for these factors, the natural, biologically-based propensity for some subjects to be better placebo responders than others can be objectively identified based on the proposed clinical trials.

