6.0 RESPONSE CRITERIA

Treatment response is defined as a reduction in VAS pain intensity $>$ or equal to 20% from visit 1-visit 2 pain ratings, or by permutation testing for change in pain rating by 0.05 p-value. Such individuals are considered treatment "responders," whereas "non-responders" are defined as individuals who experience increased or stable pain levels throughout treatment periods, including reductions in pain $<$ 20% of baseline pain intensity.

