8.0 STATISTICAL CONSIDERATIONS

8.1 Summaries of Design, Endpoints, and Analysis

8.1.1 Phase II: Study Design/Study Endpoints

Enroll and randomize 220 CBP patients into the study. Stratify into placebo responders and non-responders based on brain scan results at entry. We anticipate that about 50% of the patients will be placebo responders. All participants are randomized so that 40 receive placebo treatment, 40 active medication, and 20 no treatment. If Gender Supplement is awarded then randomization is slightly different: 60 receive placebo, 60 active medication, and 20 no treatment.

We assume that placebo responders and non-responders will show differential interaction with active medication treatment. We also expect to distinguish the four groups based on brain activity at the end of the trial, and show close correspondence between predicted and actual outcomes regarding placebo responses. Additionally, placebo non-responders should show a robust medication response, especially in comparison to the placebo non-responders receiving placebo treatment. Brain activity contrasts are done as a two-way (treatment groups) repeated measures (time: start vs. end) ANOVA (2RM-ANOVA). This is the procedure we implemented recently in a longitudinal neuroimaging study of pain chronification (Baliki et al., 2012). Post-hoc comparisons then reveal: 1) A contrast of brain activity at end of treatment between placebo non-responders with and without medication treatment to identify brain activity for bottom-up modulation of chronic pain. 2) Brain regions related to chronic pain are identified as areas commonly decreased with placebo treatment for placebo responders and medication treatment for placebo non-responders. 3) Top-down placebo and bottom-up medication effects are distinguished by identifying regions that distinctly increase in activity for placebo and medication treatments based on contrasts for the same groups. 4) The no treatment group brain activity is used as a higher-level contrast, which effectively corrects for this confound.

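### The 80% accuracy rule in 2.3.2 names no arm and makes no comparison with untreated patients, so the markers could be declared validated without evidence that they are specific to placebo

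*Combined protocol and SAP*

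**What the plan says.** The validation criterion in 2.3.2 is one sentence: "These parameters will be considered validated if together are at least 80% accurate in stratifying responders from non-responders". The matching hypothesis in 2.1.2 is "The classification before study intervention will closely correspond to the responses observed at the end of treatment period". Section 6.0 begins "Treatment response is defined as a reduction in VAS pain intensity" and measures that reduction within the person, from the visit 1 to visit 2 ratings, by a 20% threshold or a permutation test at 0.05. Nothing is subtracted for change without treatment. Section 8.2.7 describes the validation of the classifier and compares no arms.

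The no-treatment arm has a stated purpose elsewhere. Under 2.1.1, "Individuals in the No Treatment group will be used as a negative control to control for regression to the mean", along with other confounds. Under 8.1.1, for the imaging contrasts, "The no treatment group brain activity is used as a higher-level contrast, which effectively corrects for this confound". The rationale in 1.2 is firm about why such an arm is needed: "To unequivocally state that these are placebo responses, it is necessary to have a no-treatment, observation only, control group". Section 5.3 randomises within predicted class, with 15 predicted responders and 15 predicted non-responders planned for no treatment. The Figure 1 caption expects these patients to show no change: "therefore, their pain trajectory will be constant throughout the study".

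Section 2.3.2 does not name the arm or arms in which accuracy is calculated. Section 2.2 speaks of all new participants as the validation group.

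**The concern.** Accuracy against observed improvement shows that predicted class goes with improvement. It does not show that the improvement came from placebo. If Equation 1 picks out patients whose pain would have fallen anyway, predicted class and outcome agree just as well in the placebo arm, and 2.3.2 is met. The same agreement would appear in untreated patients, but the rule does not look there.

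At stake is how the validation result may be described. The conclusion that placebo propensity is predictable would rest on a criterion that does not meet the standard set in 1.2, although the design supplies the control group needed to meet it. The longitudinal model written out in 4.4 does not fill the gap: its equation has marker-by-day terms and no arm term, although the text allows covariates to be added later.

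**Working it through.** **1. Plan's own figures.** Section 5.3 gives 210 randomised 3:3:1 and about 33% attrition to 140.
- Randomised: 210 × 3/7 = 90, 90, and 210 × 1/7 = 30. This agrees with 5.3.
- Completers: 210 × (1 − 1/3) = 140, and at 3:3:1 this is 60, 60 and 20.
- Assumption: dropout is equal across arms and predicted classes, so 30 + 30 complete on placebo and 10 + 10 untreated.

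The documents give no power or error rate for the 80% rule and no rate of improvement without treatment. The response rates below are therefore assumptions.

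**2. The rule applied to a purely spontaneous marker.** With even classes, accuracy = (share improving among predicted responders + share not improving among predicted non-responders) / 2. Suppose 80% of predicted responders and 20% of predicted non-responders improve in both arms. Accuracy is (0.80 + 0.80)/2 = 80%. The placebo-specific class difference is (0.80 − 0.20) − (0.80 − 0.20) = 0.

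The rule on 60 completers needs 0.80 × 60 = 48 correct. P(X ≥ 48) for a binomial with n = 60 is 0.58, 0.89 and 0.99 at true accuracy 80, 85 and 90%.

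**3. Improvement common to both classes.** Start from a placebo-specific 80/20 split and add a 20% chance of spontaneous improvement for everyone.
- Predicted responders: 1 − 0.20 × 0.80 = 0.84.
- Predicted non-responders: 1 − 0.80 × 0.80 = 0.36.
- Accuracy: (0.84 + 0.64)/2 = 74%.

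Shared improvement lowers accuracy. False validation requires the marker itself to predict spontaneous change.

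**4. Pooling all participants does not help.** If accuracy were the same in all three arms, a purely spontaneous marker scored on 140 completers (112 correct needed) passes with probability 0.55 at 80% and 0.96 at 85%. A placebo-specific marker (80/20 on placebo, 20/20 untreated) is penalised. Its untreated accuracy is (0.20 + 0.80)/2 = 50%, so over placebo and untreated completers it scores (48 + 10)/80 = 72.5%.

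**5. What the class-by-arm contrast can deliver.** For 80/20 on placebo against 20/20 untreated, SE = √(2 × 0.16/30 + 2 × 0.16/10) = 0.207 and 0.60/0.207 = 2.90. Power for the contrast alone is Φ(2.90 − 1.96) = 0.83. The 95% half-width is 1.96 × 0.207, about 0.40.

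The claim needs both the 80% rule and the contrast. The table gives simulated probabilities (difference of risk differences, one success and one failure added per cell, z > 1.96 in the expected direction).

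| Improving on placebo, predicted responder / non-responder (%) | Untreated (%) | Meets 80% rule | Meets both |
|---|---|---|---|
| 85/15 | 85/15 (purely spontaneous) | 0.89 | 0.026 |
| 90/10 | 90/10 (purely spontaneous) | 0.99 | 0.021 |
| 85/15 | 15/15 | 0.89 | 0.87 |
| 85/15 | 30/30 | 0.89 | 0.83 |
| 85/15 | 67.5/32.5 (half spontaneous) | 0.89 | 0.38 |
| 80/20 | 20/20 | 0.58 | 0.54 |
| 80/20 | 50/20 | 0.58 | about 0.23 |

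**The case against.** The strongest reply is that the plan already guards against spontaneous change. Pain must have lasted at least six months and must average at least 5/10 over two weeks before visit 1 and again between visits 1 and 2. Patients are checked for a marked response to rescue medication before the first scan. Response is measured from averaged ratings or by permutation. The no-treatment arm is named as a negative control in 2.1.1 and enters the brain-activity contrasts in 8.1.1. The flat untreated course in Figure 1 is presented as a prediction. Most of this stands. The entry rules reduce regression to the mean without removing it, and the control role is real. None of it enters the criterion in 2.3.2, however, and that criterion alone decides whether the markers count as validated.

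Three stronger readings are tempting.
- A reader might infer that regression to the mean, given the entry threshold, by itself produces false validation. It does not: step 3 shows that improvement shared by both classes lowers accuracy.
- A reader might infer that a spontaneous marker would be declared validated. The documents support only that it could be. This depends on reaching 80%, and nothing in them shows that Equation 1 tracks spontaneous change.
- A reader might infer that the plan never uses its untreated patients. That is wrong for 2.1.1 and 8.1.1. It cannot even be said that 2.3.2 leaves them out of the accuracy figure, because no arm is named. If pooled, they would be scored as right or wrong calls and would still not act as a control.

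It can also be said that about 20 untreated completers cannot support a firm decision. That is fair for a marker of mixed origin. It limits what a non-significant result means but is no reason to omit the comparison.

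**Conclusion.** The point holds for the validation endpoint only. As written, 2.3.2 rests on 80% accuracy alone, leaves the arm open, and contains no comparison with untreated patients. It could therefore label a marker of spontaneous improvement a placebo marker, with probability 0.58 to 0.99 over true accuracies of 80 to 90%. Requiring the class-by-arm contrast as well cuts this to about 0.02 to 0.03 at 85 to 90%, and still passes a truly placebo-specific marker of 85% accuracy with probability 0.83 to 0.87. These figures assume 60 placebo and 20 untreated completers, evenly split by class, and response rates that the documents do not supply. The change is worth making before unblinding. It affects a secondary claim and does not call the randomised comparison into question.

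**What to change.** In 2.3.2, with matching text in 8.2.7:
- compute sensitivity, specificity and accuracy in the placebo arm only, and apply the 80% rule there;
- report the same three figures for the no-treatment arm beside them;
- prespecify the predicted-class-by-arm contrast (placebo against no treatment) in pain response, with its 95% confidence interval;
- claim a placebo-specific marker only if the 80% rule is met and that interval excludes zero in the expected direction;
- if the 80% rule is met but the interval does not exclude zero, report that the markers predict improvement on placebo and that placebo specificity is not established. Do not relabel them as markers of improvement in general.

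The interval rule matters. If a larger point estimate were enough, a purely spontaneous marker would pass both criteria with probability 0.34 at 80% accuracy and 0.43 at 85 to 90%.

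The cost is endpoint wording and one analysis of data the design already collects. The drawback is precision. With about 10 untreated completers per class, a genuine marker may often fail to earn the specificity claim (joint pass probability 0.54 for 80/20 on placebo against 20/20 untreated, and about 0.23 against 50/20). A non-significant contrast must therefore not be read as evidence against specificity.
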